17. DATA ANALYSIS PLAN

Pre-Post Intervention Outcomes. Descriptive statistics, reliability indices, and pre-post effect sizes (Cohen's d) will be calculated for baseline and follow-up quantitative measures and user implementation data. Data will provide useful estimates to inform larger randomized control trials of the app. Data will also guide further app refinements.

Qualitative Interviews. Data will be analyzed thematically to understand users' experiences with the My Health Coach app and research trial. The purpose is to inform further app development. Thematic analysis focuses on identifying patterns or themes within the data. Consistent with the approach advocated by Miles, Huberman, and Saldana [15], research team members will first familiarize themselves with the data, iteratively reviewing each transcript, and independently assigning initial codes ("first-level coding"). The team will then come together and discuss, operationalize, and refine each code. We will also generate "second-level codes" which consider categories or deeper meanings among first-level codes. During this process we will examine interrelationships and networks among codes and build a preliminary thematic framework. Transcripts will then be recoded and codes refined through further discussion and consensus, as needed. Participant and group "fit" with the framework will also be assessed, with confirmatory and disconfirmatory evidence for the model examined. Participant matrices may also be utilized to examine variance in themes across participants and key demographic factors, pre-post intervention change, or usage patterns.

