4. STUDY DESIGN

Page 2 of 13

This feasibility study will use a single group design with assessment timepoints prior to the receipt of the app and 6-weeks later. Primary outcomes assessed will include quality of life, self-determination theory constructs (i.e., autonomy, competence, relatedness), self-management, and barriers to care. Acceptability of the app and trial procedures will also be assessed at the 6-week timepoint.

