5. SUBJECT POPULATION

The study population will include adults (18+) with FASD. We will aim to enroll 48 adults with FASD to achieve a final sample of 40 participants with complete data. Additional participants will be enrolled if attrition is greater than anticipated.

In prior studies conducted by the ALC, 45% of participants were from Canada, 40% from USA, 9% European countries, 5% Australia / New Zealand, and 2% African countries. As such, we anticipate the vast majority of participants in our study will also be from the US and Canada. However, some will likely come the EU and UK and fall under GDPR requirements. A "Notification for Collection and Use of Personal Data" is included in the REDCap Screening Module immediately after the Study Consent Form to inform all participants from the EU or UK about compliance with GDPR requirements.

It is also possible that some adults with FASD will have legal guardians due to decisional impairment (in either specific or global domains). For these adults to participate, their legal guardian would also need to review the study consent form and provide written permission. Legal guardianship in Canada is rare but is used sometimes for adults with FASD in the US. A question in the screening module asks about legal guardianship. For those adults who indicate they have a legal guardian, our research team will contact that person to go over the permission form and obtain the needed signature through REDCap.

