9. STUDY PROCEDURES

The project research assistant will track participants in REDCap once enrolled and will facilitate timely completion of research assessments. All participants will be encouraged to complete assessments, regardless of their level of engagement with the My Health Coach app. Actual user data from the app (whether minimal or extensive) will be important in addressing study aims.

After informed consent, participants will be asked to complete a set of baseline surveys (see details on the assessment battery below). To be most sensitive, given the unique neurobehavioral profiles of participants, administration will be flexible based on participant needs and can include surveys completed independently online, over the phone or Zoom with research staff, or through the mail. Afterwards, they will be provided information on how to install the app on their phones. Study staff will be available to troubleshoot problems with installation or app use. After 6 weeks, all participants will be re-contacted to complete follow-up surveys. User implementation data will be gathered through the app. To further assess acceptability, satisfaction, and barriers and facilitators of app use, the study research assistant will complete qualitative interviews with participants over HIPAA-complaint Zoom or telephone. Interviews will be recorded and later transcribed verbatim.

Study Assessment Battery

Measure	Baseline	6-Week
		Follow-up
Quality of Life: Personal Well-being Index – Intellectual	X	X
Disability Version		
Self-Determination: The Basic Psychological Need	X	X
Satisfaction and Frustration Scale		
Self-Management	X	X
Barriers to Healthcare Checklist	X	
FASD Education	X	
Basic Demographics	X	
Acceptability: Theoretical Framework of Acceptability		X
measure		

Page 6 of 13

Qualitative Interview on User Experience		X
--	--	---

Qualitative Interview. The semi-structured questioning route will cover the following topics: 1) overall impressions of My Health Coach; 2) experience using the app (both facilitators and barriers of use); and 3) perceived impact on their health and well-being. Interviews are expected to last about 30 minutes.

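### Does the plan need a named standardiser and a confidence interval for the pre-post Cohen's d?

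*Combined protocol and SAP*

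**What the plan says.** Section 4 describes the design: "This feasibility study will use a single group design with assessment timepoints prior to the receipt of the app and 6-weeks later". It then lists the outcomes: "Primary outcomes assessed will include quality of life, self-determination theory constructs (i.e., autonomy, competence, relatedness), self-management, and barriers to care". The assessment table in section 9 marks quality of life, self-determination (the row beginning "Self-Determination: The Basic Psychological Need") and self-management at both timepoints. The barriers checklist is marked at baseline only, so it has no pre-post d and is left out here.

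Section 5 sets the size: "We will aim to enroll 48 adults with FASD to achieve a final sample of 40 participants with complete data". It adds: "Additional participants will be enrolled if attrition is greater than anticipated".

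Section 17 is the only quantitative analysis plan: "Descriptive statistics, reliability indices, and pre-post effect sizes (Cohen's d) will be calculated for baseline and follow-up quantitative measures and user implementation data". It gives two uses: "Data will provide useful estimates to inform larger randomized control trials of the app" and "Data will also guide further app refinements". No section mentions a confidence interval or standard error for d, or the SD that forms its denominator.

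**The concern.** For paired data, Cohen's d is not one quantity. The mean change can be divided by the baseline SD, by a pooled or average SD, or by the SD of the individual changes, and the same data then give different numbers. If the choice is left open, it could be made after the results are known, and a later reader might not know which scale was used.

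Precision is the second worry. With 40 people, a moderate-looking d is compatible with almost no change or with a substantial one. Section 17 offers the results as input to larger trials, and a point estimate with no interval and an unstated scale is weak input. If a planner mistook a d on the SD of change for a between-person standardised difference, the next trial could be too small.

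**Working it through.** **Inputs.** From section 5: 48 enrolled and 40 with complete data. From section 9: three instruments measured twice. If autonomy, competence and relatedness are each scored, that is five scores (an assumption). The documents give no SD, no pre-post correlation r, no correlation between outcomes, and no alpha, power or precision target. All values of r, d, alpha and power below are therefore assumptions.

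**The plan's own figure.** The 48 and 40 imply a loss of 8/48 = 16.7%, and 40/(1 - 8/48) = 48. No dropout rate is stated, so this shows only that the two numbers agree. There is no power or precision calculation to reproduce.

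**Interval on the SD of change.** Inverting the noncentral t distribution with t = d × √40 and 39 degrees of freedom gives these 95% intervals:

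| Observed d | 95% interval |
|---|---|
| 0.2 | -0.11 to 0.51 |
| 0.3 | -0.02 to 0.62 |
| 0.5 | 0.17 to 0.83 |
| 0.8 | 0.44 to 1.15 |

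The calculation needs only d and n. A reader told that d is on this scale can obtain the interval even if none is printed.

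**Interval on the baseline SD.** SE = √(2(1 - r)/40 + d²/78). For d = 0.30:

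- r = 0.5: SE = √(0.0250 + 0.0012) = 0.162, interval -0.02 to 0.62
- r = 0.7: SE = √(0.0150 + 0.0012) = 0.127, interval 0.05 to 0.55
- r = 0.8: SE = √(0.0100 + 0.0012) = 0.106, interval 0.09 to 0.51

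Here r is needed as well as d and n.

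**Effect of the standardiser.** With equal SDs at the two timepoints, d on the SD of change = d on the baseline SD / √(2(1 - r)). A baseline-SD value of 0.30 becomes 0.30/√1.0 = 0.30 at r = 0.5, 0.30/√0.6 = 0.39 at r = 0.7, and 0.30/√0.4 = 0.47 at r = 0.8. Over a wider range it is 0.25 at r = 0.3 and 0.67 at r = 0.9. Every candidate denominator is positive, so the choice never changes the sign.

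**Chance findings.** With no true change, the probability that d on the SD of change is at least 0.2 in size is 2 × P(t₃₉ ≥ 0.2 × √40) = 0.213. For at least one of five independent scores it is 1 - (1 - 0.213)⁵ ≈ 0.70. By simulation it is 0.51 if the scores correlate at 0.7. On the baseline SD the figure runs from 0.70 (r = 0.5, independent) down to 0.16 (r = 0.8, scores correlated at 0.7). The 0.2 cut-off is not in the plan, and independence is implausible for subscales of one instrument.

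**Would an interval cure this?** Only in part. With no true change, the chance that at least one of five unadjusted 95% intervals excludes zero is 1 - 0.95⁵ = 0.23 if independent, and about 0.15 by simulation at a correlation of 0.7. An interval in a single group also cannot separate an app effect from time trend or regression to the mean.

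**Where the estimates lead.** Section 17 says the interviews are meant to inform app development. Section 15 on withdrawals says survey and user-experience feedback, including from people who did not use the app, helps to show how to improve it. Section 9 treats app usage data as important to the aims. No section lets a value of d decide a refinement, sets a threshold for it or compares it across outcomes.

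**The case for a change.** The strongest contrary argument is that section 17 itself promises estimates for larger trials. As an illustration at two-sided 0.05 and 80% power (both assumed), n per arm = 2(1.96 + 0.84)²/d² gives 175 at d = 0.30. If a planner used the SD-of-change value instead, the result would be 105 at r = 0.7 or 70 at r = 0.8. Naming the standardiser and adding an interval would cost two or three sentences, and doing so in advance removes a choice that could otherwise follow the results.

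The arithmetic stands, and so does the point that stating the scale is good practice. The argument falls short on consequence. The 105 or 70 arises only if a later planner misreads the scale; it does not arise from carrying out this plan. Descriptive statistics at both timepoints would ordinarily include means and SDs, so a reader could check which SD reproduces the reported d. The interval on the baseline SD does need r. The privacy section and the data-storage section send de-identified pre-post data to the NIAAA archive, where planners with access can compute r and any version of d. An uncontrolled change would in any case be a poor direct estimate of a between-arm effect, whichever SD divides it.

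**Conclusion.** The omission is real, but no change to the plan is needed. Followed as written, section 17 yields valid descriptive effect sizes for a feasibility study that plans no test and makes no efficacy claim. The uncertainty at 40 completers is a half-width of about 0.31 to 0.36 for d between 0 and 0.8 on the SD of change. It comes from the sample size and would be the same whether or not the plan mentioned it. The choice of standardiser can move an illustrative 0.30 to anywhere from 0.25 to 0.67 for r between 0.3 and 0.9, but it changes no sign and no conclusion that the documents provide for. The analysts can state the SD used, the interval and the pre-post correlation at reporting from data already being collected. The conclusion assumes that the report includes ordinary means and SDs and treats d as uncontrolled change. It would be different if the plan tied a decision, a threshold or a sample size directly to d, and it does not.
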